1. Description of study

Background:

Infants who excessively cry, are distressed and unsettled can have a marked impact on family life. Around 1 in 6 families are affected, it is associated with maternal depression, anxiety and loss of parenting confidence. These infant behaviors are usually self-limiting (subsiding around 12 weeks after birth) but during this difficult period many parents look for additional support. There is limited research and therefore much debate about the effectiveness of manual therapy and osteopathic care for these infants.

Aim:

To evaluate the effectiveness and healthcare cost of osteopathic care for excessively crying, unsettled and distressed infants (< 10 weeks old).

[figure not shown]
Study design:

[figure not shown]
A two-arm pragmatic randomised controlled trial to assess the effectiveness of osteopathic manual therapy on infant crying time. We will need to randomize 112 parent(s)/carers and their infants to either: i) Osteopathic manual therapy with best usual care advice and support or, ii) Light non-specific touch attention control (equal time spent with infant) with best usual care advice and support. Parents will be blinded to whether their infant receives the manual therapy care or not. The cost of the delivery of the intervention will be determined and compared with data about the cost of other care.

Population: Healthy infants under 10 weeks old, reported by their parent(s)/carers as excessively crying, unsettled and distressed and difficult to console using the Rome IV criteria (> 3 hours of crying per day, for 3 days for 1 week or more). Infants with diagnosed health conditions for which they are receiving medical treatment, or who would not normally be suitable for osteopathic treatment will be excluded from the study.

Outcomes: The primary outcome is reduced average daily infant crying time over 14 days, collected via parent reported diaries. Secondary outcomes are: i) Parental self-efficacy ii) Parent perceived global improvement iii) Satisfaction and experience with treatment and iv) Adverse events.

Diagram 1. Study scheme flow chart

2. Source documents

Crying diary (participant self-report)

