| pharm7_txt | fq3.4.1 | Pharm & Supplements | Open text | String |
| help_belief_end | fq3.6 | Help belief at day 14 | Dichotomous | 0=no, 1=yes |
| experience_end | fq4.1 | Experience at day 14 | Ordinal | 1= very good, 2=fairly good, 3=neither good nor bad, 4=fairly poor, 5=very poor |
| satisfaction_end | fq4.2 | Satisfaction | Ordinal | 1=very satisfied, 2=fairly satisfied, 3=Neither satisfied nor dissatisfied, 4=fairly dissatisfied, 5=very dissatisfied |
| allocation_guess | fq4.3 | Participant's guess about allocation | Nominal | 0=Control treatment (TTR), 1=Test treatment (GTR), 2=Don't know/unsure |

2. Diary and group allocation entries

Dataset name: group.csv (one line per participant)

Source: Castor & Main investigator

Format: csv

- Group allocation is named A and B without the statistician knowing which group is which until after the analysis is complete.
- Per protocol analysis is completed from the detailed description of each deviation.

Details for data format

| Variable | Source | Description | Type | Levels |
|---------------|------------------------|--|-------------|-----------------------------|
| id | diary | UID | Numerical | integer |
| pilot | Data manager | Origin of the data | Dichotomous | 0=Main trial, 1=Pilot phase |
| group | Castor ECD | Group allocation | Dichotomous | Blinded to statistician |
| perprotocol | Participant log | Management was in accordance to protocol | Bi-nomial | 0=No, 1=Yes |
| deviation_txt | Principle investigator | Text description of protocol deviation | String | |

Dataset name: diary.csv (one line per day per participant)

Source: Crying diaries, crude data reported hourly

Format: csv

Details for data format

| Variable | Source | Description | Type | Levels |
|----------|--------|--|------------|---------|
| id | diary | UID | Numerical | integer |
| h6 | diary | Crying time from 6AM to 7AM (mins) | Continuous | minutes |
| h7 | diary | Crying time from 7AM to 8AM (mins) | Continuous | minutes |
| h8 | diary | Crying time from 8AM to 9AM (mins) | Continuous | minutes |
| h9 | diary | Crying time from 9AM to 10AM (mins) | Continuous | minutes |
| h10 | diary | Crying time from 10AM to 11AM (mins) | Continuous | minutes |
| h11 | diary | Crying time from 11AM to 7AM (mins) | Continuous | minutes |
| h12 | diary | Crying time from 12AM to 7AM (mins) | Continuous | minutes |
| h13 | diary | Crying time from 1PM to 2PM (mins) | Continuous | minutes |

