Statistical blinding will be assured to generate summary variables and set the final analysis for between group differences. Once the final statistical coding is defined and validated by the TSC, the true group identity will be revealed and additional descriptive information on treatment will be provided.

- Coding allocation to random A, B to blind first step of statistical analysis
- Treatment description included in separate dataset to be coded with different IDS than main dataset.

5. Outcome measures

Primary Outcome measure

Crying time diary

The main outcome is daily crying time in minutes. This can be measured for crying times from the first day after treatment to the thirteenth day after treatment. Daily crying time is obtained by adding hourly reported crying times from 6AM to 5:59AM the next day. D-1 is computed from the hourly reported crying time on the day prior to the treatment if the entire day is completed. When incomplete, it is replaced by the parent reported 24h baseline crying time (castor.csv). Daily crying time is considered as missing if any of the time hour slots has missing values within the day.

The primary outcome is the between group average difference in crying time from day 1 after the treatment to day 13 after the treatment. Repeated measures random linear mixed effect adjusting for baseline crying time, expectations for treatment outcome and infant's age is used to estimate the between group difference.

If diaries only report the presence of crying during each hour slot, then each time slot is replaced by the corresponding median reported crying time for infants that were crying during that hour on that specific day of follow-up.

Secondary Outcome measure

Parent Confidence

Changes of parent confidence will be measured using the Parent Confidence Score at baseline and 14 day follow up. This score relies on 15 questions about parenting confidence with a likert scale of 4 choices (0 to 45 points). Changes over time will be measured at an individual level by adding the baseline value as a dependant variable in the mixed effect model. Movement of 6 points or more is to be considered as meaningful.

Global change

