|--------------|---|-----------|-----------|-----------|
| | 10 | 15 | 30 | 60 |
| 0.8 | 636 | 284 | 72 | 18 |
| 0.9 | 852 | 380 | 96 | 24 |
| 0.95 | 1054 | 468 | 118 | 30 |

Table 4 : Sample size estimates without loss to follow up.

8. Statistical Analysis

All analysis will be intent-to-treat except for a secondary per protocol analysis on the primary outcome. All *P* values will be two sided, and the significance level is set at 5%. We will use STATA15 to precode the entire analysis prior to data collection (.do file). Deviations from the initial statistical plan will be recorded on the statistical output report.

Computing new variables

Protocol deviation

A new variable will be computed to identify deviations from protocol. Any participant who dropped-out, missed out a planned treatment, received external osteopathic care during the follow-up, or did not complete the diary daily are considered as participants who deviated from the protocol.

Unexpected reactions and adverse events

Serious adverse events, sae, will be reported as a total number for each group and as a risk ratio.

Serious adverse events will be monitored throughout the trial and reported by either the osteopaths or the participant parent.

Detailed reporting of unexpected reactions from follow-up and from the follow-up questionnaire are to be summarised to describe the presence of any unexpected reactions during the follow-up period.

Treatment description

A new set of variables is to be merged from detailed description of treatments during each visit and summarize whether each subset of care was provided or not.

Parent confidence scale

Parent confidence scale at baseline (pcs_b) and at 14 days (pcs_e) are computed from the 15 individual questions. Likert scales are scored 0 to 3 points. Scores for Q13 are inverted. Values for not applicable in Q1 and Q9 are given the score of 2. The points are then added up.

For descriptive purposes, the parent confidence scale at baseline can be compared with the following ranges:

- Non-clinical range 40 or more
- Mild clinical range 36-39
- Moderate clinical range 31-35
- Severe clinical range 31 or less

Missing data

Where participants withdraw, we will compare the characteristics of those withdrawing against those who remain in the study. Furthermore, we will do an:

- overall descriptive analysis of missing data searching for patterns,
- compare between group differences in missing data,

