- Analyse potential correlations between missing data in diary and overall summary measures.

Missing data for hourly entries will not be replaced (e.i. not missing total at random) unless parents did not report minutes in an explicit was. Graphical representations are replaced by estimates of hourly crying time. Reported crying within a hourly time slot without specification on the duration is replaced by the median observed crying time from other reported crying for that specific time slot (i.e. hour of the day and day of the trial).

Given the nature of the analysis, missing data within the diary will only reduce the power but should not affect the overall analysis.

For a diary to be considered, at least 7/14 days need to be filled in. Furthermore, best-case, and worst-case scenario will be simulated for the primary outcome implementing lowest and highest values for missing data (see sensitivity analysis).

Descriptive analysis

Descriptive statistics will be used to summarise the characteristics of participants in each arm of the trial. This will include baseline values, treatment schedules, compliance and follow-up. We will show number and percentage or mean and standard deviation for categorical and normally distributed continuous variables respectively. For data severely deviating from a normal distribution, we will present median and interquartile ranges. Probability of observed between groups difference will be provided using either Fisher's exact test, Chi2 test, and or Student's t-test.

Primary outcome analysis

We will analyse the primary outcome of crying time (e.i. individual daily measures of mean crying time in minutes) using random-effects multilevel linear regression. Crying time will be entered as the response variable (dependant) and the link function is identity. Therefore, lack of independence for measures from the same participant will be accounted for. To improve statistical power, the following explanatory variables are to be added to improve the modelling of the between-group differences

- baseline crying time (continuous),
- expectations from treatment (ordinal)
- and age of infants at entry (continuous).

To account for missing data, the data can be categorized and treated as nominal.

Results will be reported as between group difference in crying time in minutes with a 95% confidence interval. Statistical inference for significance of effects of the intervention will be calculated using Wald Chi² test.

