Mixed effect linear regression will be used to test continuous secondary outcomes. Categorical response variables using Likert scales (i.e. global change, parent satisfaction) will be considered as ordinal and non-parametrical tests (Mann Whitney U test) will be used to test between group differences. When possible (results from fractional polynomials), the outcome is to be dichotomised and the link function will be logit. Between group changes in parenting confidence score will compare changes from baseline by entering baseline score as an explanatory variable.

Proportion of participants who reported at least one adverse event will be compared between groups using a Fisher exact test. The same approach will be used to compare unexpected reactions (distress, crying, unsettled, vomiting, difficulties feeding, difficulties sleeping, other).

For cost of treatment, we will determine the mean number of treatments per infants in the trial and per group, the mean number of treatments will be multiplied by the average cost of an osteopathic treatment in UK pounds, determined by the latest data from the Institute of Osteopathy census.

Descriptive exploratory analysis

- Analyse trends over time using fractional polynomials.
- Adjust for osteopath level variables if between osteopath heterogeneity.

- Description of eventual correlation between years of experience and treatment effects (i.e. analyse of trend and comparison for cut-off at 3 or less years versus 4 or more).
- Investigate eventual association between post-graduate training and treatment outcome (interaction term).

Complementary confirmatory analysis

- A sensitivity analysis without imputed median values for crying times in time slots were parents reported crying will be run.
- A sensitivity analysis to adjust for recruiting site (ESO, UCO, Private practice, Swiss and Australian sites).
- A sensitivity analysis is planned to verify that the observed results hold in the worst- and best-case scenarios for missing data. The 25th and 75th percentile are to be used to replace missing data (25th for one group and 75th for the other) before running the primary analysis.
- If baseline imbalance (p -value <0.10) is observed, a secondary analysis with adjustment for these variables will be run to confirm results.

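### The SAP's deviation rule counts any incompletely kept diary as a protocol deviation, which conflicts with its care-based per-protocol flag and with its own 7-of-14-day diary rule

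*SAP*

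**What the plan says.** Three places in the SAP bear on who is per protocol.

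- **Section 8, Computing new variables, Protocol deviation.** A computed variable marks as a deviator "Any participant who dropped-out, missed out a planned treatment, received external osteopathic care during the follow-up, or did not complete the diary daily". One criterion is enough.
- **Section 3, item 2, group.csv.** A separate variable, perprotocol (0/1), comes from the participant log and is described as "Management was in accordance to protocol". A free-text field holds each deviation, and the section adds: "Per protocol analysis is completed from the detailed description of each deviation".
- **Section 8, Missing data.** For the main analysis the diary threshold is lower: "For a diary to be considered, at least 7/14 days need to be filled in".

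On the role of the analysis, section 8 opens with: "All analysis will be intent-to-treat except for a secondary per protocol analysis on the primary outcome". The per-protocol analysis is later listed under "Complementary confirmatory analysis". Section 5 sets what counts as a usable day: "Daily crying time is considered as missing if any of the time hour slots has missing values within the day".

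**The concern.** A per-protocol analysis is meant to compare infants who received the care they were allocated. Diary completion says nothing about that. With the clause in place, an infant treated exactly as allocated whose parent left one day unfilled is per protocol by the group.csv description and a deviator by the computed variable. The SAP does not say which of the two governs, so two analysts following it could build different sets.

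The clause also discards data that the SAP regards as usable. The mixed model takes whatever days are present, and the 7/14 rule admits partial diaries. Demanding a full diary in the per-protocol analysis brings no better adherence to treatment, and it costs sample size.

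Two consequences are possible. The set may become much smaller than adherence alone would make it. And if diary gaps relate to how much the infant cries, the set is selected on the outcome being compared, so a result that differs from the primary analysis, or agrees with it, would be hard to interpret.

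**Working it through.** **Inputs from the SAP.** Mean 120 min, SD 45, difference 30 min, 90% power, two-sided 5%, 48 infants per arm, 112 randomised (section 7); primary outcome over days 1 to 13 (section 5). The SAP gives no rate of incomplete diaries or missed sessions, so every rate below is an assumption.

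**The plan's own figure.** n per arm = 2 × (1.960 + 1.282)² × 45² / 30² = 47.3, so 48. This reproduces the SAP. An even split of 112 is 56 per arm.

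**One infant, three rules.** Take an infant treated as allocated, all sessions attended, no outside osteopathic care:

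| Diary days filled | Main analysis (7/14 rule) | group.csv flag (management) | Protocol deviation variable |
|---|---|---|---|
| 14 | in | per protocol | not a deviator |
| 7 to 13 | in | per protocol | deviator |
| under 7 | out | per protocol | deviator |

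The middle row is the conflict, and it follows from the text without any assumed rate.

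**Possible shrinkage, days missing independently.** Share of diaries complete over 13 days = (1 − m)^13, where m is the share of days missing:

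- m = 1%: 0.99^13 = 0.878, about 84 of 96 infants
- m = 3%: 0.97^13 = 0.673, about 65 of 96
- m = 5%: 0.95^13 = 0.513, about 49 of 96

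**Possible shrinkage, gaps clustered within families.** A beta-binomial with within-family correlation 0.3 (assumed) has s = 1/0.3 − 1 = 2.333 and b = (1 − m)s. The share complete is the product over k = 0 to 12 of (b + k)/(s + k). This gives 0.86 at m = 3% and 0.78 at m = 5%.

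**If one blank hour makes a day incomplete, as in section 5.** There are 13 × 24 = 312 slots. With 0.2% of slots blank independently, 0.998^312 = 0.54 of diaries are complete. At that same rate practically every infant still has at least 7 complete days of 14.

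**Effect on power.** For a simple comparison of two means with 56 per arm, power for 30 min is 94%. If half are kept (28 per arm) it is 70%, and the 95% half-width is 1.96 × 45 × √(2/28) = 23.6 min against 16.7.

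**Possible bias if exclusion depends on crying.** Let crying be Normal(μ, 45) with μ = 120 (control) and 90 (test), and let a fraction f of infants under 60 min be excluded. With z = (60 − μ)/45 and P = Φ(z), the retained mean is [μ − f(μP − 45φ(z))] / (1 − fP). For f = 0.5:

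- Control: P = 0.091, retained mean 123.9, 4.6% excluded
- Test: P = 0.252, retained mean 98.2, 12.6% excluded
- Difference: 25.6 min instead of 30

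Other cases with the same rule in both arms: f = 0.1 gives 29.3; f = 0.2 gives 28.5; f = 1 gives 18.9. Excluding half of those under 60 and half of those over 150 gives 21.6, with 17.2% lost in each arm. With no true effect, any rule applied alike in both arms gives 0. A spurious difference needs selection that differs by arm: in a simulation with no effect and assumed retention of 40% or 80% by outcome, losing settled infants in the test arm only gave about 10 min against the test arm, and opposite rules in the two arms gave about 20.

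**The case against.** The case for leaving the plan alone has several sound parts.

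- **Low stakes.** The per-protocol analysis is secondary, confined to the primary outcome, and the primary analysis is intent-to-treat with partial diaries. Every per-protocol set is formed after randomisation and open to selection. This stands and limits the consequence.
- **The set is not spelled out.** The SAP never states that the per-protocol set is exactly the non-deviators of section 8. That is the evident reading, but the need to infer it supports stating one definition.
- **Gaps may cluster.** Independent missing days overstate the loss if a few families account for most gaps. This stands, and the clustered figures above reflect it.
- **Missingness is already examined.** The SAP compares it between groups, relates diary gaps to summary measures and runs best- and worst-case scenarios. None of that changes who enters the per-protocol set.

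Three stronger readings do not stand. A reader might infer that the rule does select infants on outcome, because section 1 calls the condition self-limiting and settled infants might stop attending or recording. No section links missed sessions, diary gaps or outside care to crying, and what a planned treatment is may be set in the protocol, which is not at hand. A reader might also infer that an infant given the other arm's intervention stays per protocol, since section 8 does not list it. The group.csv log and deviation text could capture it, so the documents establish only that the two definitions need reconciling. Finally, a reader might infer that the analysis would falsely support the treatment. The same-rule scenarios shrink a real effect and give 0 when there is none.

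**Conclusion.** The point holds as a defect of definition. The diary clause measures recording rather than care, disagrees with the group.csv flag, and is stricter than the 7/14 rule, so correctly treated infants with 7 to 13 diary days are analysed in the primary analysis and labelled deviators. This rests on the text alone.

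The size is conditional. At 3% to 5% missing days, about 67% to 51% of diaries are complete if days are independent, and about 86% to 78% under an assumed within-family correlation of 0.3. Attenuation of a true 30-minute difference ranges from under 1 minute to about 11 in the same-rule scenarios, and applies only if exclusion depends on crying. Sharp shrinkage and bias are possibilities, not findings. The change is worth making because it is cheap and the analysis is listed as confirmatory, but the primary result does not depend on it.

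**What to change.** In section 8, Protocol deviation:

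1. Delete the diary-completion criterion. Apply the same 7/14-day rule and the same mixed model as in the primary analysis.
2. State one governing per-protocol definition, based on care received, and reconcile section 8 with the group.csv flag in section 3. Name receipt of the other arm's intervention explicitly as a deviation.
3. Have the flag set by staff who are blind to the diary data. Do not let it depend on whether the infant had settled, since that would tie the set to the outcome.
4. Report the number excluded by arm and by reason.
5. Describe the per-protocol analysis as supportive rather than listing it as confirmatory.

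The cost is SAP wording. The participant log, deviation text and consultation data are already planned. The downside is a per-protocol set that is less strict on completeness of data.

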| pcs_b10 | bq2.10 | Parenting confidence at baseline Q10 | Ordinal | 0=No hardly ever; 1=No, not very often; 2= Yes, some of the time; 3= Yes, most of the time |
| pcs_b11 | bq2.11 | Parenting confidence at baseline Q11 | Ordinal | 0=No hardly ever; 1=No, not very often; 2= Yes, some of the time; 3= Yes, most of the time |
| pcs_b12 | bq2.12 | Parenting confidence at baseline Q12 | Ordinal | 3=No hardly ever; 2=No, not very often; 1= Yes, some of the time; 0= Yes, most of the time |
| pcs_b13 | bq2.13 | Parenting confidence at baseline Q13 | Ordinal | 0=No hardly ever; 1=No, not very often; 2= Yes, some of the time; 3= Yes, most of the time |
| pcs_b14 | bq2.14 | Parenting confidence at baseline Q14 | Ordinal | 0=No hardly ever; 1=No, not very often; 2= Yes, some of the time; 3= Yes, most of the time |
| pcs_b15 | bq2.15 | Parenting confidence at baseline Q15 | Ordinal | 0=No hardly ever; 1=No, not very often; 2= Yes, some of the time; 3= Yes, most of the time |
| pcs_e1 | fq2.1 | Parenting confidence at 14 days Q1 | Ordinal | 0=No hardly ever; 1=No, not very often; 2= Yes, some of the time; 3= Yes, most of the time; 4= not applicable |
| pcs_e2 | fq2.2 | Parenting confidence at 14 days Q2 | Ordinal | 0=No hardly ever; 1=No, not very often; 2= Yes, some of the time; 3= Yes, most of the time |
| pcs_e3 | fq2.3 | Parenting confidence at 14 days Q3 | Ordinal | 0=No hardly ever; 1=No, not very often; 2= Yes, some of the time; 3= Yes, most of the time |

| | | | | |
|------------------|---------|--------------------------------------|-----------------------------|---|
| pcs_e4 | fq2.4 | Parenting confidence at 14 days Q4 | Ordinal | 0=No hardly ever; 1=No, not very often; 2= Yes, some of the time; 3= Yes, most of the time |
| pcs_e5 | fq2.5 | Parenting confidence at 14 days Q5 | Ordinal | 0=No hardly ever; 1=No, not very often; 2= Yes, some of the time; 3= Yes, most of the time |
| pcs_e6 | fq2.6 | Parenting confidence at 14 days Q6 | Ordinal | 0=No hardly ever; 1=No, not very often; 2= Yes, some of the time; 3= Yes, most of the time |
| pcs_e7 | fq2.7 | Parenting confidence at 14 days Q7 | Ordinal | 0=No hardly ever; 1=No, not very often; 2= Yes, some of the time; 3= Yes, most of the time |
| pcs_e8 | fq2.8 | Parenting confidence at 14 days Q8 | Ordinal | 0=No hardly ever; 1=No, not very often; 2= Yes, some of the time; 3= Yes, most of the time |

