| pcs_e9 | fq2.9 | Parenting confidence at 14 days Q9 | Ordinal | 0=No hardly ever; 1=No, not very often; 2= Yes, some of the time; 3= Yes, most of the time; 4= not applicable |
| pcs_e10 | fq2.10 | Parenting confidence at 14 days Q10 | Ordinal | 0=No hardly ever; 1=No, not very often; 2= Yes, some of the time; 3= Yes, most of the time |
| pcs_e11 | fq2.11 | Parenting confidence at 14 days Q11 | Ordinal | 0=No hardly ever; 1=No, not very often; 2= Yes, some of the time; 3= Yes, most of the time |
| pcs_e12 | fq2.12 | Parenting confidence at 14 days Q12 | Ordinal | 3=No hardly ever; 2=No, not very often; 1= Yes, some of the time; 0= Yes, most of the time |
| pcs_e13 | fq2.13 | Parenting confidence at 14 days Q13 | Ordinal | 0=No hardly ever; 1=No, not very often; 2= Yes, some of the time; 3= Yes, most of the time |
| pcs_e14 | fq2.14 | Parenting confidence at 14 days Q14 | Ordinal | 0=No hardly ever; 1=No, not very often; 2= Yes, some of the time; 3= Yes, most of the time |
| pcs_e15 | fq2.15 | Parenting confidence at 14 days Q15 | Ordinal | 0=No hardly ever; 1=No, not very often; 2= Yes, some of the time; 3= Yes, most of the time |
| gc_end | fq3.1 | Global change at day 14 | Ordinal | 1=completely recovered, 2= much improved, 3= slightly improved, 4= No change, 5= Slightly worse, 6= Much worse, 7= vastly worse |
| ur_reported | fq3.2 | Concerns | Bi-nomial | 0=no, 1=yes |
| ur_typeX | fq3.3 | Concern type | Bi-nomial (7 variables) | 1- more distress 0= no, 1= yes 2- more crying 0= no, 1= yes 3- more unsettled 0= no, 1= yes 4- more vomiting 0= no, 1= yes 5- difficulties feeding 0= no, 1= yes 6- difficulties sleeping 0= no, 1= yes 7- other 0= no, 1= yes |
| ur_type7_txt | fq3.3.1 | Other concerns | Open text | String |
| other_careX | fq3.5 | Other care | Bi-nominal (8 variables) | 1- GP 0= no, 1= yes 2- A&E 0= no, 1= yes 3- unplanned hospital admission 0= no, 1= yes 4- other osteopath 0= no, 1= yes 5- paediatrician 0= no, 1= yes 6- pharmacist 0= no, 1= yes 7- lactation consultant or midwife 0= no, 1= yes 8- other 0= no, 1= yes |
| other_care8_txt | fq3.5.1 | Other care | Open text | String |
| pharmX | fq3.4 | Pharm & Supplements | Bi-nominal (7 variables) | 1- Prescribed medicine 0= no, 1= yes 2- Anti-gas drops 0= no, 1= yes 3- Herbal supplements 0= no, 1= yes 4- Probiotics 0= no, 1= yes 5- Non-cow or ant-allergenic formula milk 0= no, 1= yes 6- Omeprazole 0= no, 1= yes 7- Other 0= no, 1= yes |

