- A sensitivity analysis adjusting for number of sessions, counselling and adjunctive treatment will be done to verify that the observed differences are not due to imbalance in patient management other than the tested intervention.
- Per protocol analysis.

9. Results analysis

Provisional tables

Table 1 Baseline characteristics for each group. GTR=, TTR=, SD=standard deviation

| Characteristics | Test group (GTR) N=xx | Control group (TTR) N= xx | Group imbalance (p-values) |
|---|-----------------------------|---------------------------------|----------------------------------|
| Females; n (%) | | | |
| Age of infant; n (%) | | | |
| 1–14 days (1–2 weeks) | | | |
| 15–28 days (3–4 weeks) | | | |
| 29–42 days (5–6 weeks) | | | |
| 43–56 days (7–8 weeks) | | | |
| 57–70 days (9–10 weeks) | | | |
| 71–84 days (11–12 weeks) | | | |
| Infant weight in kg; mean (SD) | | | |
| At birth | | | |
| At baseline | | | |
| Excessive crying, distress or unsettlement prior 24h; mean (SD) | | | |
| Age of mother in years; mean (SD) | | | |
| Siblings; n (%) | | | |
| None | | | |
| 1 | | | |
| 2 | | | |
| 3 or more | | | |
| Co-parenting; n (%) | | | |
| Parenting Confidence Score; n (%) | | | |
| Non-clinical range (40 or more) | | | |
| Mild clinical range (36-39) | | | |
| Moderate clinical range (32-35) | | | |
| Severe clinical range (31 or less) | | | |
| Expected response to osteopathic care; n (%) | | | |
| Very well | | | |
| Well | | | |
| Unsure | | | |
| Not very well | | | |
| Not well | | | |
| Missing | | | |

* Significant group imbalance at baseline

Table 2 Effects of treatment on crying time in minutes

| Outcomes | Test group (TTR) N=xx | Control group (GTR) N= xx | Adjusted * between group difference | Unadjusted between group difference |
|----------------------------------|------------------------------|---------------------------------|--|--|
| | Mean (Std.Err) | Mean (Std.Err) | Mean (CI 95%; P-value) | Mean (CI 95%; P-value) |
| Mean daily crying time (minutes) | | | | |
| From day 1 to day 13 | | | | |
| From day 1 to day 6 | | | | |
| From day 7 to day 13 | | | | |
| Daily crying times (minutes) | | | | |
| Day before treatment | | | | |
| Treatment day | | | | |
| Days after treatment | | | | |
| Day 1 | | | | |
| Day 2 | | | | |
| Day 3 | | | | |
| Day 4 | | | | |
| Day 5 | | | | |
| Day 6 | | | | |
| Day 7 | | | | |
| Day 8 | | | | |
| Day 9 | | | | |
| Day 10 | | | | |
| Day 11 | | | | |
| Day 12 | | | | |
| Day 13 | | | | |

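### The Parent Confidence Score is reversed on Q12 in the data dictionary and on Q13 in the scoring rule, so unless the instrument reverses both, at least one item counts in the wrong direction

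*SAP*

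**What the plan says.** **Storage.** In the castor.csv dictionary (SAP section 3), Q12 is the only item coded in reverse. The baseline row reads "Parenting confidence at baseline Q12 | Ordinal | 3=No hardly ever; 2=No, not very often; 1= Yes, some of the time", and the day-14 row for Q12 has the same reversed coding. Q13 is coded like the other items at both time points; the day-14 row reads "Parenting confidence at 14 days Q13 | Ordinal | 0=No hardly ever; 1=No, not very often".

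**Computation.** Under the parent confidence scale heading of section 8, each of the 15 items scores 0 to 3 and the points are summed. The only reversal named there is "Scores for Q13 are inverted".

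**Model.** Section 5 (Parent Confidence) measures change by "adding the baseline value as a dependant variable in the mixed effect model". Section 8 (Secondary outcomes analysis) compares change between groups "by entering baseline score as an explanatory variable". The primary-outcome text of section 8 uses the word dependant for the response variable.

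**Bands.** Section 8 gives "Moderate clinical range 31-35" and starts the severe range at 31 and below. Table 1 in section 9 gives "Moderate clinical range (32-35", with severe again at 31 or less.

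**The concern.** A programmer who takes the stored file and applies the scoring rule ends with two reversed items, Q12 from the file and Q13 from the rule. Nowhere does the SAP say that two items are reverse-worded. If the instrument has one, the other item subtracts from confidence where it should add.

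The score is the first-listed secondary outcome, and the rule applies to every parent at both time points. A wrongly directed item adds noise, shrinks a real group difference and moves parents between the clinical ranges shown in Table 1. Section 8 says that the analysis is to be coded in advance, so the rule could pass into the code unexamined.

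The two statements about baseline describe different models in the plan's own vocabulary, and a score of 31 belongs to two ranges in section 8. Both are smaller matters, but they belong to the same outcome and the same edit.

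**Working it through.** **Inputs from the SAP.** 15 items, each 0 to 3; total 0 to 45; meaningful change 6 points (section 5); non-clinical range 40 or more and mild range 36-39 (section 8); stored coding of Q12 and Q13 (section 3); reversal of Q13 (section 8).

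**The plan's range.** 15 × 0 = 0 and 15 × 3 = 45, as stated. Reversal turns x into 3 - x, which also runs from 0 to 3. The range is therefore 0 to 45 whichever items are reversed, and a range check cannot detect a wrong direction.

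**Error in a total.** Let x be the item's correct score. Scored the wrong way it becomes 3 - x, an error of (3 - x) - x = 3 - 2x. For x = 0, 1, 2, 3 this is +3, +1, -1, -3. A fully confident parent scores 45 - 3 = 42. A true 40 to 42 with that item at 3 is recorded as 37 to 39 and moves from the non-clinical to the mild range.

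**Error in an individual change.** With correct item scores b at baseline and e at day 14, the error is (3 - 2e) - (3 - 2b) = 2(b - e), which runs from -6 to +6.

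**Error in a mean difference.** Assume that all items move equally. A true 6-point difference is 6/15 = 0.4 per item. With one item wrong, 14 × 0.4 - 0.4 = 5.2 (13/15 of the truth). With two wrong, 13 × 0.4 - 2 × 0.4 = 4.4 (11/15).

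**By what the instrument requires**, applying both steps as written and taking the other 13 items as correctly stored:

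| Items the instrument reverses | Wrong after both steps | Error in a total | Error in a change | True 6 shows as |
|---|---|---|---|---|
| Q12 and Q13 | none | 0 | 0 | 6 |
| Q12 only | Q13 | -3 to +3 | up to ±6 | 5.2 |
| Q13 only | Q12 | -3 to +3 | up to ±6 | 5.2 |
| neither | Q12 and Q13 | -6 to +6 | up to ±12 | 4.4 |

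**Baseline in the model.** Let D be the true day-14 difference; the expected baseline difference is 0 by randomisation. If both scores are responses and only a group main effect is fitted, its expected value is (0 + D)/2 = D/2. The SAP gives no SD or correlation for this score, so the following simulation of 300 trials rests on assumed values: D = 3, SD 6, correlation 0.5, 48 per arm.

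| Model | Mean estimate | SD of estimate |
|---|---|---|
| Baseline as covariate | 3.02 | 1.05 |
| Baseline as response, group main effect only | 1.52 | 0.96 |
| Baseline as response, group-by-time | 3.03 | 1.17 |

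Only the main-effect version halves the effect. The group-by-time version is unbiased but less precise than the covariate model.

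**Bands.** Only a score of exactly 31 is ambiguous in section 8. Table 1 has no overlap.

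**The case against.** The dictionary describes storage and section 8 describes a later step. If Q12 and Q13 are both negatively worded, reversing one at storage and the other at computation gives a correct total. A reader might infer that one of the two places must be wrong. The SAP does not support that, because it does not show the item wordings. For the same reason a reader should not conclude that one of the reversals is to be deleted: if both items are reverse-worded, deleting one would create the error. This part of the objection stands. What it leaves is an unexplained discrepancy, since neither place says that two items are reversed.

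The size can also be overread. A 3-point shift needs an extreme answer on that item. Scoring is the same in both arms, so the error alone creates no group difference where none exists; the expected loss is about 13% of a real one if items move equally. The item-level answers are kept in castor.csv, so the score can be recomputed. This limits the damage but does not tell the programmer which rule to follow.

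On the model, a reader might infer that the plan halves the treatment effect. It does not say so. Halving needs baseline as a response, no group-by-time term, and the main effect reported as the result, and no section specifies that. Section 8 states the covariate form plainly, so the word in section 5 is probably a slip. It still contradicts section 8 as written. The band overlap affects one score value in a descriptive classification.

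**Conclusion.** The point holds as an unresolved scoring conflict. The SAP as written reverses Q12 and Q13, while each place names only one of them, and the coding recurs at both time points. Unless the instrument reverses both, at least one item is scored the wrong way. With one such item, totals err by -3 to +3 and individual changes by up to 6 points, and a true 6-point difference shows as about 5.2, the last figure on the assumption that all items move equally. The document cannot settle which case applies.

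The baseline wording is a contradiction to correct, with no demonstrated bias. The band overlap is a minor descriptive correction. Crying time, the primary outcome, does not use this score. Severity: should-fix.

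**What to change.** 1. Check the instrument's item wordings and scoring key. List every reversed item once in the SAP.
2. Apply each reversal exactly once, either at storage or at computation. Make the baseline and day-14 rows of the castor.csv dictionary and the section 8 rule agree, and match the code to them.
3. In section 5, make baseline score an explanatory variable, as in section 8: day-14 score on group plus baseline score.
4. In section 8, use the Table 1 bands: moderate 32-35, severe 31 or less.

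The cost is SAP wording and a few lines of code. No new data are needed.
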